The use of the device used in this clinical study has been determined to present a non-significant risk in accordance with 21 CFR 812.3 for the intended use in this study.

Potential benefits to participating individuals

Subjects may benefit by achieving visual improvement of their erythematotelangiectatic rosacea as a result of treatment in this study. Not all subjects may have complete clearance of their erythematotelangiectatic rosacea.

DATA ANALYSIS

Copies of Case Report Forms and photographs will be collected by the sponsor during the monitoring visit when appropriate and will be used for analysis of efficacy and safety.

Efficacy

The efficacy of combined Vbeam Prima PDL and topical RHOFADÉ cream for improvement in erythematotelangiectatic rosacea compared to baseline will be assessed by clinician erythema assessment, subject self-assessment, and Investigator and subject assessment, using a Global Aesthetic Improvement 5-point scale and subject satisfaction 5-point scale.

Safety

Safety of treatments will be evaluated throughout this study. Each treatment area will be evaluated for severity of purpura, edema, erythema, hyperpigmentation, hypopigmentation, blistering and scarring. All clinical response and complications observed either immediately following each treatment or at follow-up visits will be noted on the data forms. These data will be descriptively tabulated by treatment area.

Pain scores will also be assessed for safety.

Interim and Final Data Analysis

Interim analysis can be performed at any time and used to terminate the study should it seem necessary to do so.

 Candela Corporation Confidential	Pilot Study to Evaluate Combined Vbeam[®] Pulsed Dye Laser Treatment and RHOFADÉ™ (oxymetazoline hydrochloride) Topical Cream for Erythematotelangiectatic Rosacea			
	Protocol #	DHF24671	Rev. Date	June 11, 2018

ETHICS AND GOOD CLINICAL PRACTICE

This study will be carried out in compliance with the following:

- Syneron Candela Standard Operating Procedures.
- Declaration of Helsinki, concerning medical research in humans (Recommendations Guiding Physicians in Biomedical Research Involving Human Subjects, Helsinki 1964, amended Tokyo, 1975, Venice 1983, Hong Kong 1989, Seoul 2008 and Brazil 2013).
- US Code of Federal Regulations (Title 21CFR including parts 50, 56 and 812 governing informed consent and IRB regulations)
- International Conference on Harmonization (ICH) Harmonized Tripartite Guideline for Good Clinical Practice (GCP), 1996.

QUALITY ASSURANCE AND STUDY MONITORING

Study Monitoring/Auditing/Inspection

The Study Monitor will be responsible for monitoring the study sites to review the data being collected. The sponsor shall implement and maintain quality control and quality assurance procedures with written standard operating procedures (SOPs) to ensure that the trial is being conducted and data are generated, documented and reported in compliance with the protocol, Good Clinical Practice (GCP) and applicable regulatory requirements. Visits will be made prior to the initiation of the study, at scheduled intervals throughout the study, and at termination of the study.

Once enrollment and treatments have begun, monitoring visits will take place more frequently pending enrollment and study activities.

The sponsor and site will maintain regular phone and e-mail correspondence throughout the study to confirm compliance of study procedures.

The investigator/institution agrees to allow the monitor and other authorized personnel direct access to source data/documents for trial related monitoring, the clinical supplies storage/dispensing area and to provide all documents in the Investigator Regulatory Binder for review, and to assist site auditors in their activities if requested. Requests by the United States Food and Drug Administration (FDA) or regulatory agencies of other countries to inspect the study site may be made after adequate notification. The investigator may be required to assist the regulatory inspectors in their duties, if requested.

ADMINISTRATIVE PROCEDURES

Control & Disposition of the Study Device

The study device will be used according to the instructions of the Sponsor.

 Candela Corporation Confidential	Pilot Study to Evaluate Combined Vbeam[®] Pulsed Dye Laser Treatment and RHOFADÉ™ (oxymetazoline hydrochloride) Topical Cream for Erythematotelangiectatic Rosacea			
	Protocol #	DHF24671	Rev. Date	June 11, 2018

Informed Consent

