HIV	human immunodeficiency virus
ICH	international conference on harmonization
IRB	independent review board
J	Joule
mJ	milliJoule
mm	millimeter
SAE	serious adverse event
SOP	standard operating procedure
Tx	Treatment
NSR	Non-Significant Risk
PIH	post-inflammatory hyperpigmentation

STUDY SYNOPSIS

Table 1 - Study synopsis

Proprietary Name	Candela Vbeam® Prima Pulsed Dye Laser System Allergen RHOFADÉ™ (Oxymetazoline Hydrochloride) Cream
Intended use	Vbeam – treatment of benign cutaneous vascular lesions, such as facial and leg telangiectasia and rosacea. RHOFADÉ™ (oxymetazoline hydrochloride) cream, 1% is indicated for the topical treatment of persistent facial erythema associated with rosacea in adults.
Design	Prospective, two-arm randomized, baseline-controlled, pilot study.
Study population	Up to 60 healthy male or female adult volunteers seeking facial treatment for erythematotelangiectatic rosacea, 18 to 75 years of age.
Study duration	The expected total duration of this study is up to 1 year.
Sites and Investigators	Two investigational sites.
Study Design:	
Subjects in this study will be randomized to one of two treatment arms:
 
Arm 1: subjects will receive three (3) monthly Vbeam PDL facial treatments at 4-week (\pm 1 week) intervals. Subjects will apply RHOFADÉ topical cream once daily for 4 weeks, with a 2-day wash-out period, prior to the 1st Vbeam PDL treatment. Subjects in Arm 1 will continue with daily use of RHOFADÉ topical cream during the study, according to the study protocol, with a 3-day wash-out period prior to each PDL treatment. Subjects in Arm 1 will apply RHOFADÉ topical cream in-office immediately following each Vbeam PDL treatment.
 
Arm 2: subjects will apply RHOFADÉ topical cream once daily for the duration of the 6-month study. Subjects will not receive laser therapy.
 
At the 1-week post first PDL treatment follow-up visit (1wk Post Tx.1 FU), subjects will be assessed for immediate treatment response and duration of treatment response.
 
Both arms will be evaluated at each study visit (1, 2, 3 and 6 months post baseline visit). The 6-month follow-up is at (2 months following the third PDL treatment for Arm 1 and after 6 months of continuous drug therapy for Arm 2.
 
Methodology described in the protocol to evaluate efficacy and safety of treatments will be carried out at each visit at the clinic.

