Inclusion/ Exclusion Criteria	X				
Subject # Assignment	X				
Randomization to Study Arm	X				
Pregnancy Urine test	X				
Vbeam PDL test spots, (optional) – Arm 1	X	X		X	
Change to Medical History		X	X	X	X
Photographs, prior to any treatments		X	X	X	X
VISIA photographs, prior to any treatments (optional)		X	X	X	X
Clinician erythema assessment (CEA), prior to any treatments	X	X		X	X
Subject self-assessment (SSA), prior to any treatments	X	X		X	X
Vbeam PDL Treatment – Arm 1		X		X	
Tx Pain Assessment – Arm 1		X		X	
Immediate Treatment Response – Arm 1		X		X	

Visit	Screening /Baseline	Tx 1*/ 1-month FU	1-week (± 2 days) Safety Evaluation	Tx 2 - 3 / 2 & 3-Month FU Visits (4± 1 week)	6-Month (± 2 weeks) FU
Photographs, 10 mins post any treatment (optional) – Arm 1		X		X	
Global Aesthetic Improvement (GAI)		X		X	X
Vessel size assessment		X		X	X
Subject Satisfaction Questionnaire		X		X	X
Adverse Events and Serious Adverse Events	X	X	X	X	X
End of participation (Termination)					X

*For Arm 1, the 1st PDL treatment will be scheduled at approximately 4 weeks following the screening visit.

Screening Procedures

- A brief relevant medical history will be obtained to address inclusion/exclusion criteria for the study.
- Clinician erythema assessment (CEA) and subject self-assessment (SSA) will be obtained to address inclusion criteria for the study. Subjects with “moderate” or “severe” (Grade 3 or 4) are eligible for study participation (*Appendix II*).
- Pregnancy will be assessed for female subjects based on their last menstrual period, ability to become pregnant (surgical sterilization, birth control), and whether they have plans to become pregnant during the 6-month study period.
- The subject will undergo a standard skin exam to determine if they meet the study criteria.
- If the subject meets the criteria for the study, he or she will discuss with the study staff the study procedures, risks, benefits, and commitments associated with enrollment into the study. The staff will then review the consent form in detail with the subject, after which the subject will be given ample time to review the form. The subject will sign a consent form after the subject fully understands the possible risks/benefits of the study and wants to participate in study. The person conducting the session and the investigator will subsequently sign the consent form.

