 - Treatment pulses will be delivered at the threshold for nonpurpuragenic settings.
- Subjects will be instructed to report any discomfort and/or comments during and post treatment. Discomfort will be rated on a scale from 0 = no pain to 10 = worst imaginable pain using the NRS scale (*Appendix III*).
- Immediate clinical response post-treatment will be recorded for: purpura, edema, erythema, and blistering, based on a predefined scale (*Appendix IV, Table 3*).
- Post-treatment photographs (optional) may be taken, approximately 10 mins post treatment, to document post treatment effects such as the collapse of blood vessels, or to document post treatment purpura, erythema, etc.

- Subjects will be instructed on post-treatment care, including the use of sunscreen.
- Subjects in Arm 1 will apply RHOFADE topical cream immediately (in-office) following the PDL treatment. If subjects find it irritating to the skin to apply Rhofade immediately after PDL treatment, then they may apply it within 24 hours of subsequent treatments.

1-Week Post-Treatment 1 Safety Evaluation:

Subjects in Arm 1 will be scheduled for a 1-week (± 2 days) safety evaluation following the first PDL treatment. The following procedures will be conducted during this visit:

- A brief relevant medical history review for any changes from baseline.
- Skin evaluation of treatment area.
- Photographs of treatment area.
- Adverse event reporting.

Follow-up Study Visits:

The following procedures will be conducted during the 1-, 2-, 3- and 6-month study visits for subjects in both Arms 1 & 2:

- A brief relevant medical history review for any changes from baseline.
- Skin evaluation of treatment area.
- Photography will be performed according to the same procedure used at the baseline visit.
- VISIA photography (optional) may be performed according to the same procedure used at the baseline visit.
- Clinician erythema assessment (CEA) and subject self-assessment (SSA) will be recorded prior to treatment (*Appendix II*).
- Assessment of improvement (pretreatment) will be recorded by the investigator and subject using the Global Aesthetic Improvement Scale (GAI) —*Appendix IV, Table 4*.
- Improvement in vessel size will be evaluated by investigator—*Appendix IV, Table 5*.
- Subject satisfaction will be reported —*Appendix IV, Table 6*.
- Treatment will be performed (Arm 1).

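### Severity is promised for seven skin signs and duration of response at 1 week, but the schedule scores only four signs, only immediately after laser treatment

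*Combined protocol and SAP*

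**What the plan says.** The synopsis (Table 1, Study Design) states that at the follow-up one week after the first PDL treatment "subjects will be assessed for immediate treatment response and duration of treatment response". It does not define duration.

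The body of the protocol describes that visit as follows: "Subjects in Arm 1 will be scheduled for a 1-week (± 2 days) safety evaluation following the first PDL treatment". Its procedure list has four items: change in medical history, "Skin evaluation of treatment area", photographs and adverse event reporting. The same skin evaluation appears in the list for the 1-, 2-, 3- and 6-month visits. It has no scale, no list of signs and no row in Table 2.

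The scored reaction is set out under PDL Treatment Procedure and repeated under Follow-up Study Visits: "Immediate clinical response post-treatment will be recorded for: purpura, edema, erythema, and blistering, based on a predefined scale". The scale is Appendix IV, Table 3, which runs from 0 (absent) to 3 (severe). In Table 2 the row "Immediate Treatment Response – Arm 1" is marked at the Tx 1 and Tx 2-3 columns and is blank at 1 week and at 6 months.

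The Safety paragraph of Data Analysis is wider: "Each treatment area will be evaluated for severity of purpura, edema, erythema, hyperpigmentation, hypopigmentation, blistering and scarring". It adds that clinical responses and complications "observed either immediately following each treatment or at follow-up visits will be noted on the data forms", and that the data will be tabulated descriptively.

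**The concern.** The synopsis and the analysis section name measurements that the schedule does not collect in a defined way. Pigment change and scarring would not be expected to show in the minutes after a laser pulse, and those minutes are the only time the scale is applied. How long purpura or edema lasts is the kind of information the 1-week visit appears to exist for, yet no score is taken there.

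Safety of the combination is a stated objective. The protocol itself warns that some adverse effects of laser treatment may be permanent. If sites follow Table 2, a blank for hypopigmentation or scarring in the final table could mean that the sign was looked for and not found, or that nobody recorded whether they looked. That distinction cannot be recovered once the visits have passed.

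**Working it through.** No power, alpha or sample-size figure is involved. The check is a comparison of sections and a count.

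| Item | Promised in | Scheduled score | What is left |
|---|---|---|---|
| Purpura, edema, erythema, blistering, immediately after PDL | Data Analysis (Safety); safety endpoints | Table 3 scale at Tx 1, 2 and 3 | Nothing missing |
| The same four signs at 1 week | Synopsis (response and its duration) | None | Unscored skin evaluation, photographs, AE reports |
| Hyperpigmentation, hypopigmentation, scarring | Data Analysis (Safety) | None at any visit | Unscored skin evaluation, data-form notes, photographs, AE reports |

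**Counts**
- Signs promised a severity rating: 7. Signs with a scheduled score: 4. Without one: 7 − 4 = 3.
- Scoring occasions per Arm 1 subject: 3, all immediately after treatment. Number at the 1-week visit: 0.
- Visits after the first PDL session that list a skin evaluation: 1 week and 2, 3 and 6 months, so 4. Number where signs are scored at that evaluation: 0. The scores at 2 and 3 months describe the reaction to that day's treatment, not what remains from the previous one.

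**If response means efficacy.** The mismatch remains. CEA, SSA, GAI and vessel size are also blank in the 1-week column of Table 2.

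**Whether AE reporting fills the gap.** AEs are collected at every visit. The Anticipated Adverse Effects paragraph names all three unscored signs. The AE record holds onset date, severity and resolution date. The route has four limits:
1. Of the two AE definitions in that section, the more detailed one restricts AEs to events that the investigator relates to the device or study procedures.
2. Severity grades are defined only for unanticipated effects, whereas these three signs are anticipated.
3. The AE grades are mild, moderate, major and severe, with severe covering death, life-threatening illness or lasting disability. Table 3 uses absent, mild, moderate and severe. The two cannot simply be merged into one seven-sign table.
4. An AE report records what was found. It contains no scored zero.

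**Whether a 1-week score above 0 would measure duration.** It would not. One look after Tx 1 gives persistence at that time. The denominator must be subjects who had the sign immediately after Tx 1. Erythema needs separate handling, because inclusion criterion 2 admits only subjects with CEA (and SSA) of 3 or 4: redness at 1 week may be the disease rather than the laser reaction.

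**The case against.** The strongest reply is that the protocol already provides for follow-up recording. Data Analysis says that findings at follow-up visits go on the data forms, a skin evaluation is listed at each of those visits, and Table 3 names no signs, so nothing confines it to four. AE records carry severity and dates, so severity and duration can be derived for any event that is reported. The case report forms are not among the documents and may contain the missing fields. All of this stands, and it limits the point. It does not supply a defined, systematic score with recorded zeros.

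A reader might infer more than the documents support, in four ways:
- **That the safety analysis cannot be produced.** It is a descriptive tabulation. The four scored signs, pain scores and reported AEs can all be tabulated.
- **That missing duration data block that analysis.** Duration of response appears only in the synopsis. It is not an endpoint, not a safety objective and not part of Data Analysis.
- **That delayed response is a separate endpoint left unmeasured.** In the safety endpoints it sits inside the AE item, so the plan assigns it to AE reporting.
- **That enrolling Fitzpatrick types I-VI shows a high risk of pigment change.** The documents give no such figure. They exclude a history of pigmentary disorders, keloids or abnormal wound healing, and excessive tanning, and they call for nonpurpuragenic settings. The case for scoring rests on telling absence from non-assessment, not on a presumed rate.

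**Conclusion.** The concern holds as a mismatch between what is promised and what is scheduled. Three of seven signs have no scheduled severity score at any visit. None of the seven is scored at 1 week, although the synopsis promises an assessment of response and its duration there. The descriptive safety analysis remains feasible but would be incomplete for delayed signs and for persistence of the reaction.

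This is a minor point in a descriptive pilot. It does not touch the primary endpoints or the comparison between arms. It is worth correcting because the data are lost if not taken at the visit and the remedy is small. The conclusion assumes that the case report forms follow Table 2 and the visit lists. If they already score all seven signs at follow-up, only the protocol text needs to be aligned.

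**What to change.** For Arm 1:
- At the skin evaluation already held at 1 week and at the later follow-up visits, score all seven signs from Data Analysis on the existing Table 3 scale (0-3), zeros included, before any treatment that day. Add the row to Table 2.
- For purpura, edema and blistering, report the number still above 0 at 1 week among subjects who scored above 0 immediately after Tx 1. Show both counts, since the denominators may be small at nonpurpuragenic settings. Call this persistence, not duration, and add AE resolution dates where available.
- Do not count erythema above 0 as a persisting reaction. Compare it with the level before treatment, which needs the same scale at the skin evaluation before Tx 1, or report it separately.
- Tabulate hyperpigmentation, hypopigmentation and scarring by visit, keeping scored zeros apart from missing scores.
- Reconcile the synopsis sentence on the 1-week visit with what is then collected.

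The cost is about one CRF page and a few minutes per visit. The added scores number 7 signs × 4 visits = 28 per Arm 1 subject, plus 7 if all signs are also scored before Tx 1. No visit is added and treatment is unchanged.

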- Use with caution in patients with cerebral or coronary insufficiency, Raynaud's phenomenon, thromboangiitis obliterans, scleroderma, or Sjögren's syndrome.
- Advise patients to seek immediate medical care if signs and symptoms of acute narrow-angle glaucoma develop.

The most common adverse reactions (incidence > 1%) are application site dermatitis, worsening inflammatory lesions of rosacea, application site pruritus, application site erythema, and application site pain. In clinical trials, adverse reactions occurred in 1% - 2% of subjects treated with RHOFAD[™] through 4 weeks of treatment. In the long-term (open-label) clinical trial, the rates of adverse reactions over a one-year treatment period were as follows: worsening inflammatory lesions of rosacea (3%), application site dermatitis (3%), application site pruritus (2%), application site pain (2%), and application site erythema (2%). Subjects with persistent erythema along with inflammatory lesions were allowed to use additional therapy for the inflammatory lesions of rosacea [8].

STUDY DESIGN

This is a prospective, two-arm randomized, baseline-controlled, pilot study to evaluate the efficacy of combined Vbeam PDL and topical RHOFAD[™] cream for improvement in erythematotelangiectatic rosacea.

[figure not shown]
Up to 60 healthy male or female subjects will be enrolled at two investigational sites. All subjects will undergo an assessment of their general health. Following enrollment, subjects will be randomized to a study arm. Subjects in Arm 1 will receive RHOFADÉ topical cream at the screening visit and will be instructed to apply it daily for 4 weeks prior to the first PDL facial treatment. Arm 1 subjects will receive three (3) monthly PDL facial treatments at 4-week intervals. Subjects will apply RHOFADÉ topical cream once daily during the 6-month study, according to the study protocol, with a 3-day wash-out period prior to each PDL treatment. Immediately following the PDL treatment, subjects in Arm 1 will apply RHOFADÉ topical cream in-office. If subjects find it irritating to the skin to apply RHOFADÉ immediately after PDL treatment, then they may apply it within 24 hours of subsequent treatments.

Arm 2 subjects will receive RHOFADÉ topical cream at the screening visit and will be instructed to apply it daily for 6 months of continuous use until the 6-month post-baseline follow-up visit. . Subjects in Arm 2 will not receive laser therapy.

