A one-week post first PDL treatment safety follow-up visit will be conducted (1wk FU post Tx.1) for Arm 1 subjects. In addition, efficacy and safety evaluations will be performed at each study visit (1, 2, 3 and 6 months post-baseline visit), as shown in Figure 1 below..

Erythema severity will be assessed at baseline and at each study visit. Improvement in erythema severity will be assessed at each post baseline visit. Additionally, investigator and subject questionnaires will be completed. Photography will be performed at each study visit under visible light conditions of the front full face, right and left 45-degree profile and right and left 90-degree profile. VISIA photography may also be performed for spectrometry measurements (optional). Safety assessments will be conducted at each study visit.

Study Flowchart

Primary Efficacy Objective:

To evaluate the efficacy of combined Vbeam Prima PDL treatment and topical RHOFADÉ cream for improvement in erythematotelangiectatic rosacea, at the 6-month follow-up compared to baseline and compared to Arm 2 at the 6-month follow-up (RHOFADÉ drug therapy only).

Secondary Efficacy Objectives:

- Evaluate the efficacy of combined PDL and topical RHOFADÉ cream (Arm 1) for improvement in erythematotelangiectatic rosacea at each treatment visit (pre-treatments 2 and 3) compared to baseline.
- Evaluate the efficacy of combined PDL and topical RHOFADÉ cream (Arm 1) for improvement in erythematotelangiectatic rosacea compared to topical RHOFADÉ cream only (Arm 2) at each study visit (pre-treatments 2 and 3 and 6-month follow-up for Arm 1 and at the 2-, 3-, and 6-month follow-up visits for Arm 2).
- Evaluate subject satisfaction at each study visit (1, 2, 3 and 6 months post-baseline).
- Evaluate overall improvement (investigator and subject) at each study visit (1, 2, 3 and 6 months post-baseline).
- Evaluate improvement in vessel size (investigator) at each study visit (1, 2, 3 and 6 months post baseline visit).

Safety Objectives:

- Evaluate the safety of combined PDL treatment and topical RHOFADÉ cream (Arm 1) during the study.
- Evaluate comfort level associated with PDL treatment (Arm 1).

 Candela Corporation Confidential	Pilot Study to Evaluate Combined Vbeam[®] Pulsed Dye Laser Treatment and RHOFADE[™] (oxymetazoline hydrochloride) Topical Cream for Erythematotelangiectatic Rosacea			
	Protocol #	DHF24671	Rev. Date	June 11, 2018

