9. Subject has an infection or is suffering from current or has a history of significant skin conditions in the treated area or inflammatory skin conditions, including, but not limited to: photodermatoses, active acne, excessive skin dryness, psoriasis, eczema, rash, open wounds, varicella scars, open lacerations or abrasions and active cold sores or herpes sores prior to treatment (duration of resolution as per the Investigator’s discretion) or during the treatment course.

10. Having a known anticoagulative or thromboembolic condition or taking anticoagulation medications one week prior to and during the treatment course (to allow inclusion, temporary cessation of use might be requested as per the subject's physician discretion).
11. Use of non-steroidal anti-inflammatory drugs (NSAIDS, e.g., ibuprofen-containing agents) one week before and after each treatment session.
12. Subject has a history of pigmentary disorders, particularly tendency for hyper- or hypo-pigmentation.
13. Subject has a history of keloid scarring or of abnormal wound healing.
14. Subject has a known photosensitivity to the device's laser wavelengths, history of ingesting medications known to induce photosensitivity, or history of seizure disorders due to light.
15. Subject has undergone any surgical, light-based therapy or RF procedures in the treatment area within 3 months of treatment or during the study.
16. Having undergone any other surgery in the treated area within 3 months of treatment (or more if skin has not healed completely) or during the study.
17. Subject has a tattoo or permanent make-up in the treated area.
18. Subject has systemically used retinoids or antioxidants within 1 month of treatment or during the study.
19. Excessively tanned in areas to be treated or unable/unlikely to refrain from tanning during the study.
20. Participation in a study of another device or drug within three months prior to enrollment or during the study.
21. As per the Investigator's discretion, any physical or mental condition which might make it unsafe for the subject to participate in this study.

Study Procedures

The following table provides a summary of the required study visits and the procedures and assessments performed at each visit.

Table 2: Study Schematics

Visit	Screening /Baseline	Tx 1* / 1-month FU	1-week (± 2 days) Safety Evaluation	Tx 2 - 3 / 2 & 3-Month FU Visits (4± 1 week)	6-Month (± 2 weeks) FU
Informed Consent	X				
Medical History	X				

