- Once the consent form is signed, the subject will be assigned the next consecutive subject number and will be randomized to a treatment arm.
- Women capable of childbearing will undergo a urine pregnancy test.

- Skin type will be recorded using the Fitzpatrick Scale.
- Test spots may be performed (optional) for subjects in Arm 1 to determine the subject's response to selected treatment parameters. Test spot locations will be selected by the investigator.
- Subjects in Arms 1 & 2 will be provided with RHOFADE topical cream and instructed to apply once daily, according to the drug insert instructions: apply a pea-sized amount once daily in a thin layer to cover the entire face (forehead, nose, each cheek, and chin) avoiding the eyes and lips.
- The RHOFADE topical cream will be applied daily for 4 weeks prior to the first PDL facial treatment.
- Subjects must discontinue topical use for a 3-day washout period prior to each PDL treatment.

Pre-Treatment PDL Care

In order to minimize pain during laser irradiation, subjects will be offered to use topical anesthetic cream (EMLA), which will be applied to the skin surface 30-60 minutes prior to laser irradiation.

PDL Treatment Procedure

- Treatments will be performed every 4 (± 1) weeks. Subjects in Arm 1 must discontinue topical use for a 3-day washout period prior to each PDL treatment.
- Laser treatment procedures will conform to all laser safety instructions and should be conducted per the procedure described.
- The investigator, all personnel in the treatment room and the subject will wear protective eyewear, appropriately rated for the device wavelength(s) being operated.
- Based on the subject's response to the test spot evaluation (optional) or experience from treatment of prior subjects in this study or in practice, the investigator will select the parameters used for treatment, based on the threshold for nonpurpuragenic settings.
- Parameters include choice of: the 12 mm or 15 mm spot size, the laser fluence, the duration of the laser pulse exposures and the cooling procedure. The investigator will treat the face with the parameters chosen and will document the parameters.
- The treatment area will be photographed before each treatment and at each post-treatment follow-up visit. Optional photography can include photos at 10 minutes (approximately) after each treatment.
- All subjects will be treated as follows:
 - The 12 mm or 15 mm spot size will be used.

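### Arm 1 is scored after a cream wash-out at months 1, 2 and 3 but on daily cream at month 6, so its by-visit CEA, SSA and GAI results do not measure the same thing

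*Combined protocol and SAP*

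**What the plan says.** Study Design has Arm 1 use the cream once daily through the 6-month study, "with a 3-day wash-out period prior to each PDL treatment". PDL Treatment Procedure makes the stop mandatory: "Subjects in Arm 1 must discontinue topical use for a 3-day washout period prior to each PDL treatment". For the first session the synopsis (Table 1) gives a different length: "with a 2-day wash-out period, prior to the 1st Vbeam PDL treatment". Either length leaves Arm 1 off cream at that visit.

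Table 2 places the first laser session at the 1-month visit and the others under "Tx 2 - 3 / 2 & 3-Month FU Visits (4± 1 week". It shows no laser session at month 6, and no wash-out is stated before that visit. Arm 2 applies the cream continuously to month 6.

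On timing within a visit, Follow-up Study Visits states: "Clinician erythema assessment (CEA) and subject self-assessment (SSA) will be recorded prior to treatment". For GAI it states: "Assessment of improvement (pretreatment) will be recorded by the investigator and subject using the Global Aesthetic Improvement Scale (GAI". Vessel size carries no such label; only its place in the list, ahead of the treatment step, suggests when it is scored.

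The Secondary Efficacy Objectives then ask for results by visit: "Evaluate overall improvement (investigator and subject) at each study visit (1, 2, 3 and 6 months post-baseline" and "Evaluate improvement in vessel size (investigator) at each study visit (1, 2, 3 and 6 months post baseline visit". They also compare Arm 1 with baseline before laser sessions 2 and 3, and Arm 1 with Arm 2 at months 2, 3 and 6. The primary objective uses month 6, against baseline and against Arm 2. The Efficacy paragraph of Data Analysis lists the assessments and does not mention cream state.

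**The concern.** The Background section says the cream is thought to reduce redness by vasoconstriction, and redness is what CEA and SSA score. Whether cream was in use when the score was taken is therefore part of what the score measures. In Arm 1 that condition changes between month 3 and month 6, while the objectives describe every visit as efficacy of the same combined treatment.

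Two sets of results are affected. Within Arm 1, a gain after month 3 may be resumed cream rather than laser, and a flat line may be fading laser benefit offset by cream. Between arms, the month-2 and month-3 comparisons put Arm 1 at the end of a wash-out against Arm 2 on cream. If the cream effect is lost in the wash-out, that understates what adding the laser does.

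**Working it through.** The plan states no power, alpha, SD or by-visit model, so there is no figure of its own to reproduce. The check has two steps.

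**1. Scheduled cream state at scoring** (synopsis, Study Design, Table 2, PDL Treatment Procedure, Follow-up Study Visits)

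| Visit | Arm 1 | Arm 2 |
|---|---|---|
| Baseline | study cream not yet dispensed | study cream not yet dispensed |
| Months 1, 2, 3 | end of wash-out | on cream |
| Month 6 | on cream | on cream |

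Arm 1 is off cream at 3 of 3 visits in months 1 to 3 and at 0 of 1 at month 6. Month 6 is the only post-baseline visit at which the arms share a state.

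**2. Additive illustration** (all effect sizes assumed)

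Let *L* be the laser effect at month 3, *f* the part of it lost by month 6, and *c* the part of the cream effect present in daily use but gone at the end of wash-out, all in CEA grades. Any cream effect that survives wash-out is common to both arms and visits and cancels. Negative values mean less redness.

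- Arm 1, month 3: −*L*. Month 6: −(*L* − *f*) − *c*. Change: *f* − *c*.
- Arm 2, both visits: −*c*.
- Arm 1 minus Arm 2, month 3: −*L* + *c*. Month 6: −(*L* − *f*), free of *c*.

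With *L* = 0.5:

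| *c* | *f* | Arm 1 change, month 3 to 6 | Between arms, month 3 | Between arms, month 6 |
|---|---|---|---|---|
| 0 | 0 | 0.00 | −0.50 | −0.50 |
| 0.25 | 0 | −0.25 | −0.25 | −0.50 |
| 0.5 | 0 | −0.50 | 0.00 | −0.50 |
| 1.0 | 0 | −1.00 | +0.50 | −0.50 |
| 0.25 | 0.25 | 0.00 | −0.25 | −0.25 |
| 0.5 | 0.5 | 0.00 | 0.00 | 0.00 |
| 0.25 | 0.5 | +0.25 | −0.25 | 0.00 |

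Rows 2 to 4 show an apparent late gain with no change in laser effect. Rows 5 and 6 show fading hidden behind a flat profile. Row 7 shows worsening despite the cream. Row 1 shows no artefact.

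To gauge how visible a false gain would be, assume 30 subjects in Arm 1 (half of 60; no allocation ratio is stated), stable laser benefit, and a paired normal test at two-sided 5%. The chance of a nominally significant gain is Φ(*c* / (SD/√30) − 1.96).

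- SD 0.8: SE = 0.8/√30 = 0.146. For *c* = 0.25, 0.5 and 1.0, the ratios are 1.71, 3.42 and 6.85, giving 40%, 93% and about 100%.
- SD 1.0: SE = 1.0/√30 = 0.183. The ratios are 1.37, 2.74 and 5.48, giving 28%, 78% and about 100%.

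**The case against.** The strongest reply is that no month-3-to-month-6 test, trend or durability claim is planned. Listing visits sets assessment times, and the primary time point is month 6. That is correct, and it limits the within-arm part of the point to how a by-visit table may be read. It does not answer the between-arm part, because the month-2 and month-3 comparisons are stated objectives.

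Two stronger readings are tempting, and the documents support neither.

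- A reader might infer that Arm 1 must improve at month 6 by design. That needs a cream effect lost during wash-out, present again when month 6 is scored, and larger than any laser fading. The documents give no duration of effect, no vehicle-adjusted effect (only composite success of 15% and 12% on Day 29, without vehicle rates) and no interval from last application to month-6 scoring.
- A reader might infer that the trial cannot show lasting laser benefit. That is true only of the Arm 1 series on its own. At month 6 both arms are scheduled on daily cream, and the contrast between them falls 2 to 3 months after the last session.

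It is also fair to object that the illustration is in CEA grades, on assumed inputs, for an unplanned test on a 5-point ordinal scale. GAI covers texture, vessel size and flushing, and no cream effect on GAI or on the vessel-size score is documented. These objections limit the numbers. They do not remove the switch in state.

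**Conclusion.** The point holds in a limited form. Arm 1's CEA, SSA and GAI results at months 1 to 3 are scores after wash-out, its month-6 results are scores on cream, and Data Analysis does not recognise the difference. A month-3-to-month-6 change in Arm 1 cannot be attributed to laser. If the cream effect wears off in the wash-out, the series is biased towards improvement or can hide fading. On the same condition, the month-2 and month-3 between-arm comparisons are biased against Arm 1. The primary month-6 between-arm contrast is like-for-like on cream and can show benefit of added laser.

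The direction depends on the cream effect being lost in the wash-out, and the size is unknown. For assumed losses of 0 to 1.0 grade with stable laser benefit, the false gain runs from 0 to 1.0 grade. Vessel size is left open, since neither its timing relative to treatment nor its sensitivity to the cream is stated.

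**What to change.** In Data Analysis:

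- Label each Arm 1 assessment by scheduled cream state: *end of wash-out* at months 1, 2 and 3, *on cream* at month 6.
- Describe the month-2 and month-3 results, within Arm 1 and against Arm 2, as effect after wash-out, not as efficacy of the combined regimen in use.
- Make no Arm 1 trend statement from month 3 to month 6.
- Rest inference about added laser on the month-6 between-arm contrast.
- State whether vessel size is scored before treatment.

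Two inconsistencies bear on these labels and must be reconciled. The first is the wash-out before the first laser session: 2 days in one sentence of the synopsis, 3 days before each session in Study Design and PDL Treatment Procedure. The second is the interval from the third session to the last visit: 2 months in the synopsis and Photographs section, but about 3 months by Table 2 (month 6 minus month 3).

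The cost is a few lines of text and table labels, with no change to visits or treatment. The sponsor gives up any durability reading of the Arm 1 series across months 3 to 6.
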